## **Brief Study Synopsis**

**Study Phase:** Pilot

**Primary hypothesis:** Pentoxyfylline (PTX) therapy at 1200 mg per day or the renally dose equivalent in addition to standard of care is superior to placebo in the treatment of acute renal failure (ARF) not responsive to volume resuscitation in hospitalized patients with cirrhosis.

**Study design:** Prospective, placebo-controlled, randomized pilot trial.

Each hospitalized subject will undergo pre-dosing screening with review of his or her history and physical exam from the day of enrollment and safety assessment to ensure no contraindication to use of PTX.

ARF will be defined according to the definition put forth by and validated prospectively by collaboration between the International Ascites Club (IAC) and the Acute Dialysis Quality Initiative as a rise in creatinine of 0.3 mg/dl or 50% from baseline creatinine, which will be defined as the most recent stable measurement before admission.[1]

Baseline testing will be obtained from hospitalization records, including but not limited to chemistry panel, liver function testing, urinalysis, urine electrolytes, coagulation studies, blood cultures, chest x-ray, diagnostic paracentesis, abdominal ultrasound with Doppler.

Subjects will take either placebo three times a day or PTX 400mg three times a day or 400mg twice a day for eGFR 10-50 and 400mg once a day for eGFR <10 for 14 days in addition to standard inpatient care. Treatment will be continued for 14 days unless a study endpoint has been reached at which time either PTX or placebo will be stopped.

**Total study subjects expected:** 30 patients with cirrhosis hospitalized ARF

**Duration of study:** 180 days

**Study Drugs:** PTX 400 mg tablets and placebo. The study team will not be pursuing a change in labeling or an FDA approved indication for this drug as a part of this proposal. Standard placebo provided in similar tablet forms. All investigational drugs will be prepared by the Investigational Pharmacy by inserting the active drug/placebo into larger cloaking capsules. Standard corn starch will be used inside the placebo capsule.

Randomization will be 1:1. The Investigational Pharmacy will be performing randomization and will generate the block randomization scheme.

**Endpoints:** The primary endpoint is resolution of ARF, defined as a return to baseline creatinine for 24 hours.

The secondary endpoints of progression of ARF to a different stage as defined by AKIN criteria will be assessed.[3] If a patient is enrolled at stage III ARF, they will be considered to have progressed should they be started on renal replacement therapy (RRT). Other secondary endpoints that will be assessed include change in serum creatinine from baseline to day 14, combined increase of treatment success and “partial response” which we define as serum creatinine level decreased by >50% from baseline but not to baseline without dialysis or HRS recurrence, transplant free survival at day 30 and 180, overall survival at day 30 and 180, composite survival index at day 30 and 180.

**Statistical Methods:** All analyses will be conducted based on the intention to treat population. Results will be expressed as means with standard deviations. Chi-squared and Fisher’s exact test will be used to analyze our categorical endpoints. Student’s t test and Mann-Whitney Rank Sum test will be used for secondary analysis of differences in numerical lab data. Kaplan-Meier curves will be constructed and compared by a log-rank test to assess our secondary endpoints of survival. A p value of <0.05 will be significant. Subgroup analysis will be performed by stratifying on initial AKIN stage.

**Future Study:** If there is a treatment benefit with using PTX for treatment of ARF in patients with cirrhosis, we would apply for an orphan grant from the NIH or foundation awards from the American Association for the Study of Liver Diseases for a multi or single center, randomized, double blinded placebo controlled trial. Ideally we could combine this with translational research to help better determine a mechanism of action.

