In their landmark study, Tyagi et al[28] demonstrated that PTX is effective in preventing HRS in cirrhotic patients with ascites. In their randomized placebo controlled trial of 70 patients, 35 were given PTX with improvements in serum sodium, mean arterial pressure and preservation of creatinine. Of the 12 patients who developed HRS, two patients were in the PTX arm (type-1 HRS,  $n = 2$ ) ( $P = 0.01$ ). The authors noted that patients with HRS had higher baseline TNF- $\alpha$  ( $15.3 \pm 5.8$  vs.  $10.9 \pm 4.8$  pg/ml,  $P = 0.01$ ), lower MAP ( $68.0 \pm 3.8$  vs.  $77.8 \pm 6.5$  mmHg,  $P = 0.01$ ), and sodium level ( $131.2 \pm 3.0$  vs.  $135.6 \pm 4.7$  mmol/l,  $P = 0.003$ ) than those who did not develop HRS.

To our knowledge, no study to date has investigated adding PTX to the treatment algorithm for the treatment of ARF in patients with cirrhosis despite the previously demonstrated benefit of PTX as primary prophylaxis to prevent HRS, a subtype of ARF.[27]

For all of these reasons, we propose a double blind, randomized, placebo controlled pilot trial with PTX to investigate the efficacy of PTX in treating ARF in patients with cirrhosis.

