## 2. Study Design

[figure not shown]
The proposed study is a blinded prospective, placebo controlled, randomized pilot study. Figure 1 shows the study design schematic. Subjects will be identified during their hospitalization with ARF. Each subject will undergo screening and a pre-dosing history and physical exam, and safety assessment, which will include reviewing basic blood work results and imaging from their hospitalization (CBC, CMP, INR, Blood cultures, UA and urine culture, Urine lytes, Chest x-ray, Abdominal ultrasound with dopplers, diagnostic paracentesis if ascites is present) and performing urine pregnancy testing in women of child bearing potential. Subjects will be randomized 1:1 by the Investigational Pharmacy.

Subjects will then take a 14-day course of PTX 400 mg three times a day. On day 3 there will be an in-person assessment and review of side effect profile. If there have been no serious adverse events, PTX will be continued. Additional safety assessments will be completed at day 7,10,14.

Patients will also be seen in the hospital to assess for treatment response at day 3,7,10,14. At these visits, they will have repeat blood work at the discretion of the treating physicians (e.g. CBC, CMP, INR, UA with reflex urine culture, Urine lytes,). During each assessment, primary and secondary endpoints will be measured. If an endpoint is obtained, the patient will be instructed to stop therapy.

Survival will be assessed at 30 and 180 days by telephone interviews. If subjects are discharged prior to completing 14 days of therapy, they most likely has met an endpoint (resolution, death, transplant, etc). If in the unlikely event the patient is to be discharged and they have not met an endpoint, they will be withdrawn from the study. Once the patient is discharged there will be no in person follow up evaluations.

Figure 1: Study protocol

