### 3. Subject Selection

This study will enroll 30 patients with cirrhosis hospitalized with acute or chronic liver disease and ARF as defined according to the criteria put forth by and validated prospectively by collaboration between the International Ascites Club (IAC) and the Acute Dialysis Quality Initiative as a rise in creatinine of 0.3 mg/dl or 50% from baseline creatinine, which will be defined as the most recent stable measurement before admission.[1]

All participants will be aged greater than or equal to 18 and non-pregnant because of the study drug characteristics. Patients with labeled contraindications to PTX use will be excluded.

All subjects will be initially located on the general medical floor, typically 5 central which is a GI and hepatology floor. If a subject decompensates and requires ICU level care then they will be transferred to the ICU at the discretion of the treating physician. Admission to the ICU will not impede participation status unless the patient reaches an endpoint of death, liver transplant or renal replacement therapy at which time their participation in the study will have concluded. We will not be performing initially enrollment of the patient in the ICU. We will not seek surrogate consent. If a patient is still in the ICU at day 14 they will not be considered for therapy beyond that point and therefore surrogate consent will not be required.

If a patient is unable to swallow a pill for 6 consecutive doses they will be withdrawn from the study.

Table 1 shows the exclusion criteria.

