## 7. Study Treatments

### 7.1. Investigational Drug

PTX is a vasoactive xanthine derivative and phosphodiesterase inhibitor that improves peripheral blood flow and enhances peripheral tissue oxygenation. PTX relaxes smooth muscle in peripheral vessels leading to vasodilation. PTX improves red blood cell flexibility, which allows for improved blood flow ability. Importantly, PTX promotes platelet deaggregation and decreases blood viscosity. The summative effects are a decrease in inflammatory mediators. The investigational pharmacy will be used for drug acquisition, storage, and accountability. Subjects will start the protocol with 400mg PTX three times a day for 14 days or the renally dosed equivalent (400mg BID for eGFR 10-50 and 400mg daily for eGFR <10). The investigators will not seek FDA labeling or approved indications for PTX as part of this study; therefore, no IND will be sought for the study drug use in this protocol. There are no restrictions on concurrent drugs other than those listed in the exclusion criteria in Table 1. The study drug cannot be crushed or administered through a nasogastric tube. If a patient is NPO but can swallow safely, they may receive the drug. If they are NPO and have a nasogastric tube in place they will miss the dose.

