## 8. Study Assessments

### 8.1. Schedule of Visits

The schedule of study assessments and visits is shown in Table 2.

Table 2: Schedule of visits and study protocol assessments

Visit	Screening initial assessment	Follow up assessment	"Partial response" assessment	Phone Call
Day	0	Day 3,7,10,14	Day 14, 28	Day 30,180
Initial history and physical exam	X			
ARF response assessment		X	X	X
Symptom triggered physical exam		X	X	
Interim safety assessment and pill count		X	X	
Labs and imaging	X	X	X	

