### 8.2. Primary Endpoints

ARF treatment response will be assessed according to Table 2. The PI or sub-investigators will perform all assessments and will assess for the presence of side effects or toxicities of the study drug by performing a brief history at each visit and by performing a targeted physical exam. A phone call to assess 30 and 180-day survival will be completed.

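### Placebo stays at three capsules a day while PTX drops to two or one at eGFR 50 or below, so dosing frequency discloses the arm in those subjects

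*Combined protocol and SAP*

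**What the plan says.** The Brief Study Synopsis gives the only placebo schedule in the document: "Subjects will take either placebo three times a day or PTX 400mg three times a day or 400mg twice a day for eGFR 10-50". The sentence goes on to set PTX at once a day when eGFR is below 10. Section 7.1 describes the regimen as PTX three times a day for 14 days "or the renally dosed equivalent (400mg BID for eGFR 10-50 and 400mg daily for eGFR <10". It does not mention placebo.

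Section 1 presents the study as double blind: "we propose a double blind, randomized, placebo controlled pilot trial". Section 2 calls it blinded. The masking measure described is in the synopsis: the Investigational Pharmacy puts drug or corn starch placebo into larger cloaking capsules.

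Table 2 in Section 8.1 lists "Interim safety assessment and pill count" at the follow-up visits on days 3, 7, 10 and 14. Section 8.2 says who sees the result: "The PI or sub-investigators will perform all assessments".

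Section 3 adds a rule that depends on dosing frequency: "If a patient is unable to swallow a pill for 6 consecutive doses they will be withdrawn from the study".

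**The concern.** If the arms take different numbers of capsules a day at the same eGFR, identical capsules do not protect the blind. The people who would notice are those who give doses, count pills, know the eGFR and judge response.

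The primary endpoint is a return to baseline creatinine for 24 hours, and survival is objective, so knowing the arm cannot change the measurement itself. It can act through decisions around the measurement:

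- **Sampling.** Section 2 says of the response visits that "they will have repeat blood work at the discretion of the treating physicians". How often creatinine is drawn affects whether and when a 24-hour return to baseline is seen.
- **Discharge.** Under Section 2, a subject discharged before reaching an endpoint is withdrawn, with no later in-person evaluation.
- **Adverse events.** Under Section 7.2, the PI and medical monitor judge whether a grade 3 event is drug-related, which decides whether treatment stops.
- **Renal replacement therapy.** Starting it is a clinical decision. It counts as progression for subjects enrolled at stage III (Section 5.2) and ends participation (Section 3).

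The swallowing rule differs between arms even if nobody acts on knowledge of the arm, because six consecutive doses span different lengths of time.

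**Working it through.** The plan states no figure to reproduce. The check sets the schedules side by side and then does simple arithmetic.

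**Inputs.** Frequencies and eGFR tiers: synopsis and Section 7.1. Visit days: Table 2. Six-dose rule: Section 3. Sample size of 30: Section 9. Creatinine exclusion above 4.0: Table 1 (printed as g/dL, read here as mg/dL).

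**1. Schedules as written**

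| eGFR | Placebo, capsules/day | PTX, capsules/day | Does frequency identify the arm? |
|---|---|---|---|
| above 50 | 3 | 3 | No |
| 10-50 | 3 | 2 | Yes |
| below 10 | 3 | 1 | Yes |

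A twice-daily or once-daily schedule occurs only on PTX, so it identifies PTX without knowledge of the eGFR. A three-times-daily schedule identifies placebo only to someone who also knows that the eGFR is 50 or below. Investigators and treating clinicians have that information.

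**2. Pill counts at eGFR 10-50 with full adherence** (capsules per day × days)

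| Day | Placebo (3 × day) | PTX (2 × day) |
|---|---|---|
| 3 | 9 | 6 |
| 7 | 21 | 14 |
| 10 | 30 | 20 |
| 14 | 42 | 28 |

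**3. Swallowing rule at eGFR 10-50** (6 doses ÷ doses per day). Placebo: 6/3 = 2 days. Twice-daily PTX: 6/2 = 3 days. A placebo subject who cannot swallow is withdrawn one day sooner than a PTX subject in the same state.

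**4. How many subjects.** Let q be the share with eGFR of 50 or below. The documents do not give q, so it is an assumption. Number affected = 30 × q:

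| q | 30% | 50% | 70% | 90% |
|---|---|---|---|---|
| Subjects | 9 | 15 | 21 | 27 |

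**5. Is the affected range a plausible one for this population?** The documents name no eGFR equation. Assuming CKD-EPI 2021 and ages 45 to 65:

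| Creatinine (mg/dL) | eGFR, men | eGFR, women |
|---|---|---|
| 1.2 | 67-76 | 50-57 |
| 1.5 | 51-58 | 38-44 |
| 1.8 | 41-47 | 31-35 |
| 4.0 | 16-18 | 12-13 |

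eGFR reaches 50 at a creatinine of 1.53-1.70 in men and 1.20-1.34 in women. Much of the eligible range up to 4.0 therefore falls in the twice-daily tier. eGFR reaches 10 only at 5.86-6.50 in men and 4.61-5.11 in women, above the entry limit, so in this age range nobody starts in the once-daily tier. These figures show which creatinine values are affected. They do not estimate q, because the distribution of creatinine, age and sex at entry is not given.

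**The case against.** The best reply is that the asymmetry is loose wording. The protocol sometimes writes PTX where it must mean study drug. Section 2 says "Subjects will then take a 14-day course of PTX 400 mg three times a day", which cannot be true of every subject. The PTX-only tiers in Section 7.1 are therefore weak evidence that placebo was meant to stay unadjusted, and the Investigational Pharmacy, which randomizes and prepares the capsules, could match the schedules. That is possible, but nothing in the document says so, and the one placebo schedule that is stated contradicts it. A pharmacist following the synopsis would dispense placebo three times a day at every eGFR.

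Several narrower points stand:

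- Not every observer is unmasked. A placebo subject who does not know the tiers learns nothing from a three-times-daily schedule. Near an eGFR of 50, or after creatinine has changed, the inference is also less certain, because no rule says which eGFR sets the dose.
- For this trial, the words double blind appear only in Section 1. Section 2 says blinded. Either description fails for the investigators.
- The routes to bias are indirect. The endpoint is a laboratory value, Section 2 regards discharge before an endpoint as unlikely, and grade 4 events stop treatment whatever their cause.
- The swallowing rule differs by one day, only in affected subjects, and no incidence is given.

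The plan does specify intention-to-treat analysis. That keeps subjects in their assigned arm, but it does not restore masking or supply creatinine values that were never drawn.

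**Conclusion.** The concern holds. As written, dosing frequency identifies the arm for subjects with eGFR of 50 or below, at least to investigators and clinicians who know the tiers and the eGFR. Those investigators are due to see pill counts and judge response. Subjects above 50 are unaffected, and the tier below 10 is essentially empty at entry.

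The capsule counts and the 2-day versus 3-day withdrawal clock follow directly from the stated schedules. The number of subjects affected rests on an assumed share, and the creatinine scale rests on an assumed equation and age range. The conclusion about the blind depends on neither. The resulting bias cannot be quantified from the documents.

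This must be fixed, because a lost blind cannot be restored in the analysis. The pilot's result is meant to decide whether a larger trial is sought.

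**What to change.** State in the synopsis and in Section 7.1 that the Investigational Pharmacy dispenses placebo at the same capsule frequency as PTX for the same eGFR tier, and that any change of tier during treatment applies equally in both arms. Scheduled 14-day counts at eGFR 10-50 then become 28 in each arm, and the six-dose rule takes 3 days in each.

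Filling the omitted PTX slots with placebo capsules would also work, giving 42 in each arm and a 2-day rule in each. Matching the frequency is simpler and gives fewer capsules.

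Separately, add the renal tiers to the dosing sentence in Section 2, which now gives three times a day without them. That is a drafting omission and not part of the unblinding argument.

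The cost is one sentence in each of two places, an addition to a third, and a pharmacy dispensing instruction. No extra patients, visits or procedures are needed.

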## 5. Study Objectives

This study is a randomized placebo controlled trial and is hypothesis based. Data on efficacy will be assessed.

5.1. Primary Objective: PTX is safe and effective in treating ARF in hospitalized patients with cirrhosis when added to standard of care

5.2 Secondary and Exploratory Objectives: Progression of ARF to a different stage as defined by AKIN criteria will be assessed.[3] If a patient is enrolled at stage III ARF, they will be considered to have progressed should they be started on renal replacement therapy (RRT). Other secondary endpoints that will be assessed include change in serum creatinine from baseline to day 14, combined increase of treatment success and “partial response” which we define as serum creatinine level decreased by >50% from baseline but not to baseline without dialysis or HRS recurrence, transplant free survival at day 30 and 180, overall survival at day 30 and 180, composite survival index at day 30 and 180.

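### The AKIN-progression endpoint has no rule for death or transplant before progression; read literally, such deaths count as not progressed

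*Combined protocol and SAP*

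**What the plan says.** The endpoint is defined twice in the combined protocol and SAP, in nearly the same words. The Brief Study Synopsis has: "The secondary endpoints of progression of ARF to a different stage as defined by AKIN criteria will be assessed". Section 5.2 has: "Progression of ARF to a different stage as defined by AKIN criteria will be assessed". Both add one special case, for patients enrolled at stage III: "they will be considered to have progressed should they be started on renal replacement therapy (RRT". Neither place mentions death or transplant, and neither gives a time window.

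Elsewhere, death is an event that ends follow-up. Section 3 says that ICU admission does not affect participation unless the patient "reaches an endpoint of death, liver transplant or renal replacement therapy at which time their participation in the study will have concluded". Section 2 says of patients discharged early that "they most likely has met an endpoint (resolution, death, transplant, etc". Death is also measured in its own right through the secondary endpoints "transplant free survival at day 30 and 180, overall survival at day 30 and 180, composite survival index at day 30 and 180".

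The Statistical Methods paragraph of the synopsis and section 9 call for an intention-to-treat analysis, with chi-squared and Fisher's exact tests for categorical endpoints. Neither gives a competing-event method or a rule for outcomes that cannot be observed.

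**The concern.** Death before progression is a competing event: once it happens, the stage change or RRT can no longer be seen. With every randomised patient in the denominator and only a stage change or RRT in the numerator, the text as written puts the worst outcome in the better of two categories.

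The documents make such deaths plausible within the 14-day course. Section 1 cites a life expectancy under 2 weeks for type 1 HRS, and Table 1 excludes only patients expected to live 72 hours or less. Section 2 leaves repeat blood work to the treating physicians, so worsening shortly before death may go unrecorded.

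At stake is the direction of the comparison. If PTX prevents early deaths, more PTX patients remain at risk of a recorded progression, and PTX looks worse on this endpoint. If PTX causes early deaths, it looks better. If the rule is instead left open until analysis, it would be chosen once the deaths are known.

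**Working it through.** **Plan's own figure.** None is stated for this endpoint. The total of 30 patients, 15 per arm (section 9), comes with no event rates, effect size or power, so there is nothing to reproduce.

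**Notation.** For each arm, let d be the risk of death before any recorded progression, and q the risk of progression among the other patients. All values of q and d below are assumptions.

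- Literal scoring (such deaths are not progressed): q(1 − d)
- Death counted as an event: q(1 − d) + d

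**General result.** If q is the same in both arms, the difference PTX minus placebo is:

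- literal: q(d_placebo − d_PTX)
- death counted: (1 − q)(d_PTX − d_placebo)

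For any q strictly between 0 and 1, these have opposite signs whenever the death risks differ. If d is the same in both arms, both scorings give the same difference, (1 − d)(q_PTX − q_placebo), which is zero when q is also equal.

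**Illustration, q = 0.30, d = 0.10 on PTX and 0.30 on placebo.**

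| Scoring | PTX | Placebo | Difference |
|---|---|---|---|
| Literal | 0.30 × 0.90 = 27% | 0.30 × 0.70 = 21% | PTX 6 points worse |
| Death counted | 27% + 10% = 37% | 21% + 30% = 51% | PTX 14 points better |

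Swapping the death risks between arms reverses both signs. With q = 0.50 and the same death risks, the literal figures are 45% vs 35%, and counting death gives 55% vs 65%.

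**Illustration with mortality cited in the protocol.** Section 1 cites 24.5% vs 46.1% mortality for PTX vs placebo in alcoholic hepatitis. Take q = 0.30:

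- All deaths precede progression. Literal: 0.30 × 0.755 = 22.7% vs 0.30 × 0.539 = 16.2%. Death counted: 47.2% vs 62.3%.
- Half the deaths precede progression (d = 12.25% and 23.05%). Literal: 26.3% vs 23.1%. Death counted: 38.6% vs 46.1%.

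This is a different population, so these figures show the mechanism and are not a forecast.

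**At the trial's size.** Suppose 5 of 15 progress in each arm, with 1 further death before progression on PTX and 5 on placebo.

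| Rule for these deaths | PTX | Placebo | Fisher p |
|---|---|---|---|
| Not progressed | 5/15 (33%) | 5/15 (33%) | 1.00 |
| Event | 6/15 (40%) | 10/15 (67%) | 0.27 |
| Excluded | 5/14 (36%) | 5/10 (50%) | not computed |

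The same data give three different estimates, and the plan does not choose among them.

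**The case against.** A reader might infer that the plan scores these deaths as not progressed. It does not go that far. It gives no coding rule, and intention-to-treat settles who is analysed, not how an unobserved outcome is coded. A death could be counted as not progressed, progressed, missing or excluded. What the documents support is a gap, together with an unfavourable literal reading.

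A reader might also infer that everyone who dies without dialysis is affected. That is too broad. A patient enrolled at stage I or II whose stage worsens before death has progressed without any RRT, and the RRT rule is written only for stage III at entry.

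Three further points stand in the plan's favour:

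- Deaths are not lost to the trial. Survival at days 30 and 180 is reported separately, so an imbalance would be visible beside the progression result. This does not correct the progression comparison.
- The type 1 HRS figure cannot be carried over to the whole trial. Section 1 names pre-renal azotemia and ATN as other subtypes of ARF, enrolment is on the general floor, and Table 1 excludes shock. No death rate for this trial follows from the documents.
- The problem needs unequal death risk. Section 1 reports evidence on both sides: the alcoholic hepatitis trial above, and a 335-patient trial in advanced cirrhosis with no appreciable survival difference.

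Finally, 15 patients per arm will rarely give a significant result under any rule; neither p value in the count example is below 0.05. So the documents do not support a claim that a formal conclusion would be reversed. What can reverse is the direction of the estimate.

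**Conclusion.** The point holds as a gap in the endpoint definition that should be closed before analysis. Death or transplant before progression has no stated handling, and the literal reading places a death before a recorded stage change, or before RRT in a patient enrolled at stage III, in the favourable category.

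The size cannot be taken from the documents. Under the assumed 30% progression and 10% vs 30% death before progression, the choice of rule moves the difference from 6 points against PTX to 14 points in its favour. With equal death risk, counting these deaths as events or as non-events makes no difference to the expected contrast. This is a secondary endpoint of a pilot. It still matters because the synopsis makes a treatment benefit here the basis for seeking funds for a larger trial, where the direction of the estimates will be read.

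**What to change.** Replace the definition in the synopsis and section 5.2 with: progression to a higher AKIN stage, start of RRT, or death from any cause by day 14, analysed over all randomised patients. State how a liver transplant before progression is counted. Tabulate each component by arm, with progression alone shown beside the composite.

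This wording makes three other choices that should be acknowledged as such: it replaces a different stage with a higher one, adds a day-14 window, and applies the RRT criterion to every entry stage. A competing-risk analysis specified in advance would also answer the point. Patients withdrawn at discharge (section 2), or after being unable to swallow six consecutive doses (section 3), still need a stated rule, because the composite does not score them.

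The cost is one change of definition, using outcomes the trial already follows, provided the date of death is recorded. The downside is that the composite includes some non-renal deaths and overlaps with the survival endpoints; the component table makes both visible.

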**Table 1: Exclusion criteria**

Allergy or hypersensitivity to PTX or intolerance to methylxanthines (e.g. caffeine, theophylline)
Concurrent use of nephrotoxic drugs
Age less than 18
Pregnancy
Acute or chronic renal replacement therapy at time of enrollment
Shock
TNF alpha antagonist use
Subject is institutionalized or a prisoner
Recent cerebral or retinal hemorrhage (contraindication to PTX)
Previous participation in this study
Severe or poorly controlled cardiovascular disease as determined by the principal investigator to hinder the ability to adhere to study protocols
Creatinine > 4.0 g/dL
Life expectancy $\leq$ 72 hours

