## 9. Statistical Procedures and Methods

As this is a pilot study and the benefit of PTX in the treatment of ARF has not been studied, we estimate a sample size of 30, 15 in each treatment arm, is sufficient to meet our primary and secondary endpoints. Results will be expressed as means with standard deviations. Chi-squared and Fisher's exact test will be used to analyze our categorical endpoints. Student's t test and Mann-Whitney Rank Sum test will be used for secondary analysis of differences in numerical lab data. Kaplan-Meier curves will be constructed and compared by a log-rank test to assess our secondary endpoint of all-cause mortality. A p value of  $<0.05$  will be significant. Intention to treat analysis will be performed. Subgroup analysis will be performed by stratifying on initial AKIN stage.

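### Partial response cannot be met by anyone as worded; with the >50% fall taken from enrolment creatinine, it stays closed to patients whose creatinine has at most doubled

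*Combined protocol and SAP*

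**What the plan says.** The Brief Study Synopsis (Study design) defines ARF as "a rise in creatinine of 0.3 mg/dl or 50% from baseline creatinine", "which will be defined as the most recent stable measurement before admission". Section 3 repeats this. No other baseline creatinine is defined.

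The Synopsis then states: "The primary endpoint is resolution of ARF, defined as a return to baseline creatinine for 24 hours". No tolerance around baseline is given.

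The Synopsis goes on to partial response, "which we define as serum creatinine level decreased by >50% from baseline but not to baseline without dialysis or HRS recurrence". Section 5.2 repeats it in the same words: "serum creatinine level decreased by >50% from baseline but not to baseline", subject to the same conditions on dialysis and recurrent HRS. It enters the analysis through the secondary endpoint listed as "combined increase of treatment success and “partial response". Table 2 in Section 8.1 gives it its own assessment column, at days 14 and 28.

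Section 9 adds: "Subgroup analysis will be performed by stratifying on initial AKIN stage". Section 2 says that primary and secondary endpoints are measured at each assessment and that a patient who reaches an endpoint is told to stop therapy.

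**The concern.** The definition uses one word, baseline, for the value the creatinine falls from and for the value it must not reach. Those cannot be the same number. The natural repair is to read the first as the creatinine at enrolment. That repair is not enough: a patient who enters with a modest rise gets back to the pre-admission value before creatinine has halved, so no room is left for a partial response.

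What is at stake is the meaning of the combined endpoint. For patients with smaller rises it would repeat the primary endpoint. For patients with larger rises it would offer a second way to be counted as a response. The combined rate would then depend partly on how severe the ARF was at entry, and comparisons between severity subgroups would be partly a product of the definition.

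**Working it through.** The plan has no figure of its own to reproduce here: Section 9 gives 30 patients without a response rate, effect size or power.

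**Inputs**
- B: pre-admission creatinine (Synopsis, Study design; Section 3).
- C0: creatinine at enrolment. Its use as the reference for the fall is an assumption; the documents never name it as a baseline.
- C: follow-up creatinine.
- Entry: C0 − B ≥ 0.3 mg/dl, or C0 ≥ 1.5 × B (Synopsis; Section 3).
- Upper limit: Table 1 excludes "Creatinine > 4.0 g/dL", read here as mg/dl (an assumption), so C0 ≤ 4.0.

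**Step 1: B in both places.** A fall of more than 50% from B means C < 0.5 × B. Not reaching B means C > B. No C satisfies both.

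**Step 2: the fall is measured from C0.** C < 0.5 × C0 and C > B together require B < 0.5 × C0, that is C0 > 2B.

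| B | C0 | 0.5 × C0 | Qualifying C |
|---|---|---|---|
| 1.0 | 1.5 | 0.75 | none |
| 1.0 | 1.9 | 0.95 | none |
| 1.0 | 2.0 | 1.00 | none |
| 1.5 | 2.9 | 1.45 | none |
| 2.0 | 4.0 | 2.00 | none |
| 1.0 | 2.5 | 1.25 | 1.00 to 1.25 |
| 1.0 | 3.0 | 1.50 | 1.00 to 1.50 |
| 1.0 | 4.0 | 2.00 | 1.00 to 2.00 |

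Equivalently, the fall that already reaches B is 1 − B/C0. This is 23.1% at C0/B = 1.3, 33.3% at 1.5, 42.9% at 1.75 and 50.0% at 2.0. With C0 capped at 4.0, 0.5 × C0 is at most 2.0, so no patient with B ≥ 2.0 can qualify at any eligible C0.

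A grid of eligible pairs (B from 0.50 to 3.95 in steps of 0.05; C0 up to 4.00 in steps of 0.01) agrees. The Step 1 reading is open for 0 of 10,472 pairs. The Step 2 reading is open for 0 of the 5,822 pairs with C0 ≤ 2B. These counts check the algebra; they do not estimate a share of patients.

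**Step 3: two patients, both with B = 1.0.**

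| | Patient 1 | Patient 2 |
|---|---|---|
| C0 to C | 1.9 to 1.05 | 4.0 to 1.9 |
| Share of rise recovered | 0.85/0.9 = 94% | 2.1/3.0 = 70% |
| Above B at follow-up | 5% | 90% |
| Absolute fall, mg/dl | 0.85 | 2.1 |
| Fall from C0 | 0.85/1.9 = 44.7% | 2.1/4.0 = 52.5% |
| Partial response under Step 2 | no | yes |

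**Step 4: other readings.** A tolerance on return to baseline raises the bar: with B = 1.0, a tolerance of 0.1 needs C0 > 2 × 1.1 = 2.2, and 0.3 needs C0 > 2 × 1.3 = 2.6. If peak creatinine is the reference, the condition becomes peak > 2B.

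**Step 5: a definition based on the rise.** (C0 − C)/(C0 − B) > 0.5 is the same as C < B + 0.5 × (C0 − B). This limit exceeds B whenever C0 > B, so the window is open for every eligible patient (5,822 of the 5,822 grid pairs above). Patient 1's limit is 1.0 + 0.45 = 1.45 and Patient 2's is 1.0 + 1.5 = 2.5; both become partial responders. For a rise of 0.3 mg/dl the required fall is just over 0.15 mg/dl. With B = 2.0 and C0 = 2.3 that means C < 2.15, a fall of 0.15/2.3 = 6.5%.

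**The case against.** The strongest reply is that the enrolment reference is not in the documents, so the root defect is the undefined reference and the rest is conditional. That is fair as to order. But naming C0 as the reference is the obvious clarification, and it would leave the category closed at C0 ≤ 2B, so both parts need to be settled together.

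A reader might infer several stronger things that the documents do not support:

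- **That no patient with C0 ≤ 2B could ever qualify.** Resolution has to last 24 hours. If not reaching baseline is taken to mean not meeting the primary endpoint, a brief dip would count: B = 1.0, C0 = 2.0, one value of 0.95, then 1.1. With peak creatinine as reference, a patient who worsens beyond 2B after enrolment could also qualify. Both routes are narrow, but the wording allows them.
- **That the secondary endpoint is empty.** On the enrolment reading only its partial-response component is, and only for these patients. The combined endpoint still counts treatment success; it is redundant there.
- **That recoveries are ranked in the wrong order.** This depends on the yardstick. By nearness to B, the trial's own standard for resolution, Patient 1 did better. By absolute or percentage fall, Patient 2 improved more and the order is not inverted.
- **That a severity imbalance must appear as a treatment difference.** It can, with 15 per arm and no stratified randomization described, but it need not. Severity may also affect the primary endpoint, and the net direction is unknown.

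It is also true that change in creatinine to day 14, another secondary endpoint, captures incomplete recovery in milder ARF. That softens the loss without repairing the category.

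**Conclusion.** The point holds in a limited form. Taken with the protocol's own baseline, partial response is impossible for everyone. Taken with enrolment creatinine as reference, it is closed, apart from an unsustained dip, to every eligible patient with C0 ≤ 2B, and for them the combined endpoint adds nothing to the primary. Between C0/B of 2 and 4 the window opens gradually, from nothing to C between B and 2B.

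The algebra needs no distributional assumption. The practical size does: the documents give no distribution of creatinine rises, so the share of the 30 patients affected cannot be derived. AKIN cut-offs are not given either, so I have not mapped the gap onto the planned subgroups. The limit at B ≥ 2.0 rests on reading the Table 1 unit as mg/dl.

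The primary endpoint is untouched. This is a certain defect in one component of a secondary endpoint, and it should be corrected before analysis.

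**What to change.** In the Synopsis (secondary endpoints) and Section 5.2:

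- Name two reference values: B, the pre-admission creatinine, and C0, the last creatinine before the first dose.
- Define partial response, for analysis, as more than 50% of the rise recovered, B < C < B + 0.5 × (C0 − B), without meeting the primary endpoint. Keep the present conditions on dialysis and recurrent HRS.
- State how a patient who touches B for less than 24 hours is classified.
- Report a fall of more than 50% from C0 as a descriptive line.

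The sentence in Section 2 on stopping therapy once an endpoint is obtained, and the similar one in the Synopsis, must be reconciled with the revised definition, so that it is clear whether partial response counts as an endpoint there. Otherwise a change meant for the analysis could alter who stops study drug.

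The cost is one definition in two places, plus that reconciliation, with no new data. There are two downsides. The rate becomes less comparable with trials that used a 50% fall. For minimal rises the threshold is a small change, just over 0.15 mg/dl for a rise of 0.3 mg/dl, which may be hard to separate from measurement variation.
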